## **5.2.2 Secondary Endpoints**

The secondary endpoints of this study, to provide further information on the safety and efficacy of the IMM-101 + nivolumab combination, are assessed at the end of the study and measured by:

Progression-free survival (PFS) assessed by RECIST 1.1. PFS is defined as the time between the date of the first post-Screening visit (Week 0, Visit 1) and the first date of documented progression, as determined by the Investigator from CT or MRI scan, or death due to any cause, whichever occurs first. Subjects who die without a reported progression will be considered to have progressed on the date of their death. Patients who did not progress or die will be censored on the date of their last evaluable tumour assessment. Patients who did not have any on study tumour assessments (scans) and did not die will be censored on their date of first post-Screening visit. Patients in cohort B who change therapy on study to IMM-101 + ipilimumab without documented progression by RECIST 1.1 will be censored at the date of their last evaluable tumour assessment prior to this change in therapy.

Overall survival (OS) and OS at 1 year. OS is defined as the time from enrolment (date of the first post-Screening visit (Week 0, Visit 1) to death due to any cause. Patients without a death date will be censored at the date the patient was last known to be alive. The median OS (if applicable) and OS rate at 12 months will be estimated.

- Incidence and frequency of laboratory parameter abnormalities
- Change from baseline values in laboratory parameter values
- Incidence and frequency of local injection site reactions.

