#### 6.5 CONCOMITANT MEDICATIONS

#### **6.5.1** Prohibited Medications

Medications or vaccinations specifically prohibited in the exclusion criteria are not allowed during this study. If there is a clinical indication for a medication or vaccination specifically prohibited during this study, discontinuation from study therapy may be required, with the decision to continue the patient on the study being made by the mutual agreement of the Investigator, the Sponsor and the patient.

Patients are prohibited from receiving the following therapies during the Screening and Treatment Phase of this study:

- Antineoplastic systemic chemotherapy or biological therapy
- Immunosuppressive agents, except for acute treatment of potential immune-related AEs during the study
- Systemic corticosteroids >10 mg daily prednisolone equivalent, unless for acute treatment of potential immune-related AEs during the study. Systemic corticosteroids ≤10 mg daily prednisolone equivalent for more than 2 weeks are also prohibited
- Other investigational agents
- Radiation therapy apart from to a symptomatic solitary lesion which may be allowed
  at the discretion of the Investigator and after consultation with the Sponsor. Such
  therapy is only allowable after the first scheduled tumour assessment on study, unless
  otherwise agreed with the Sponsor
- Live vaccines within 30 days prior to the first dose of study therapy and while participating in study. Examples of live vaccines include, but are not limited to: measles, mumps, rubella, chicken pox, yellow fever, seasonal flu, H1N1 flu, rabies, BCG, and typhoid vaccine

Page 40 of 98

In addition, cytokines (e.g., Interferon alpha [IFN- $\alpha$ ]), monoclonal antibodies, anti-tumour vaccines, and biological response modifiers should be used with caution when given concomitantly with IMM-101.

Any prior and concomitant therapy/medications taken up to 30 days before the first dose of study medication will be recorded in the patient's eCRF at Screening.

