### 10.2 PROGRESSION FREE SURVIVAL (PFS)

PFS is defined as the time between the date of the first post-Screening visit (Week 0, Visit 1) and the first date of documented progression, according to RECIST 1.1, as determined by the Investigator from CT/MRI scans, or death due to any cause, whichever occurs first.

Patients who die without a reported progression will be considered to have progressed on the date of their death. Subjects who did not progress or die will be censored on the date of their last evaluable tumour assessment. Subjects who did not have any on study tumour assessments (scans) and did not die will be censored on the date of first post-Screening visit. Subjects in cohort B who change therapy on study to IMM-101 + ipilimumab without documented progression by RECIST 1.1 will be censored at the date of their last evaluable tumour assessment (scan) prior to this change in therapy.

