5.13.2 Secondary Endpoints

5.13.2.1 PFS Assessed by RECIST 1.1 for Cohorts A and B

PFS will be analysed using the ITT set and analysis will be repeated for the PPS for Cohort A only.

PFS is defined in months as the time between Visit 1 and the first confirmation of progression using RECIST 1.1, or death from any cause (whichever occurs first) (date

of first progression or death – date of Visit 1 + 1). Progression is determined by the investigator using the CT or MRI scan (scheduled or unscheduled) or death due to any cause. Subjects who die without reported progression will be considered to have progressed on the date of their death.

The following censoring rules will apply:

- Subjects who did not progress or die will be right censored on the date of their last evaluable tumour assessment.
- Subjects who did not have any on-study tumour assessments (scans) and did not die will be right censored on their date of first post-Screening visit. Note that this definition is consistent with that used for [Checkmate 067](#)².
- Subjects who remain on study following radiotherapy or other prohibited treatment will be censored at their last scan assessment prior to the intervention therapy.
- Subjects in Cohort B who change therapy to IMM-101 + ipilimumab without documented progression by RECIST 1.1 will be censored at the date of their last evaluable tumour assessment prior to this change in therapy.

Summaries of PFS

Descriptive statistics will be presented for PFS. The number and percentage of subjects that are censored will be summarised, along with KM estimates for the 25th, 50th and 75th percentiles of PFS and corresponding 95% CIs. PFS will also be presented graphically using a KM plot. The proportion of subjects who have not progressed or died at three monthly intervals will also be presented.

A time to event listing will present the milestones required for calculation of each time to event efficacy parameter.

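### SAP 5.13.2.1 adds an unlisted PFS censoring rule for radiotherapy or other prohibited treatment, with no condition on earlier progression and no defined trigger

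*SAP*

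**What the plan says.** SAP 5.13.2.1 measures PFS from Visit 1 to progression by RECIST 1.1 "or death from any cause (whichever occurs first"). It then gives four censoring bullets:

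1. Subjects with neither progression nor death are censored at the last evaluable assessment.
2. Subjects with no on-study scan who did not die are censored at the first post-Screening visit.
3. "Subjects who remain on study following radiotherapy or other prohibited treatment will be censored at their last scan assessment prior to the intervention therapy".
4. Cohort B subjects who switch to ipilimumab "without documented progression by RECIST 1.1 will be censored at the date of their last evaluable tumour assessment prior to this change in therapy".

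Protocol 10.2 has counterparts to bullets 1, 2 and 4, beginning with "Subjects who did not progress or die will be censored on the date of their last evaluable tumour assessment". Protocol 5.2.2 has the same three. Neither mentions radiotherapy or prohibited treatment.

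The SAP does not define prohibited treatment. The list in Protocol 6.5.1 covers antineoplastic therapy, immunosuppressants, systemic steroids, other investigational agents, radiotherapy and live vaccines. The vaccine examples are "measles, mumps, rubella, chicken pox, yellow fever, seasonal flu, H1N1 flu, rabies, BCG, and typhoid vaccine". On steroids it adds: "Systemic corticosteroids ≤10 mg daily prednisolone equivalent for more than 2 weeks are also prohibited". Immunosuppressants, and steroids above 10 mg, given acutely for potential immune-related adverse events are exempt. Radiotherapy to a symptomatic solitary lesion may be allowed. Protocol 7.5 lets patients stay on treatment after RECIST progression under conditions.

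SAP Section 6 lists five changes from the protocol's planned analysis. This rule is not one of them.

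**The concern.** A PFS censoring rule should say what happens when the event has already occurred. Bullet 3 does not. It applies to anyone who stays on study after the intervention and sends them back to the last scan before it. If that scan is the one that showed progression, an event becomes a censoring.

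The trigger is also wider than anti-cancer therapy. A live vaccine or a long low-dose steroid course stops PFS follow-up, and a later progression or death is not counted, although the same section counts death from any cause.

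PFS is a descriptive secondary endpoint, so no error rate is involved. But the protocol and SAP say efficacy will be compared with published nivolumab data, and with 18 and 8 patients each event moves the curve visibly. A rule that departs from the protocol definition should be deliberate, unambiguous and declared.

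**Working it through.** The documents give no PFS assumption, event count or power figure, so there is no planned number to reproduce. The check compares the texts and then illustrates the size.

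**1. The four bullets side by side**

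| SAP bullet | Condition on event status | In Protocol 5.2.2 and 10.2 |
|---|---|---|
| 1. No event | no progression or death | yes |
| 2. No scans | no death | yes |
| 3. Radiotherapy or prohibited treatment | none | no |
| 4. Ipilimumab switch | no documented RECIST progression | yes |

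**2. Two illustrative patients**

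- Stable at week 12, progression at week 20, stays on study, solitary lesion irradiated at week 22. Protocol 10.2: event at week 20. Bullet 3 read literally: censored at week 20.
- Stable at weeks 12 and 20, live vaccine at week 22, progression at week 28. Protocol 10.2: event at week 28. If the vaccine counts as a prohibited treatment, bullet 3 censors at week 20 whether or not an earlier progression would take precedence.

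**3. Size by hand**

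Take 18 patients (the planned cohort A) on its scan weeks 12, 20, 28, 36, 44, 52, 60, 68 and 76, with two progressions at each. This pattern is an assumption. The Kaplan-Meier estimate is S(t) = Π(1 − d/n) over scan times up to t.

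- No recoding: S(52) = 6/18 = 0.333; median 44 weeks.
- One week-20 event recoded: 16/18 × 15/16 × 6/14 = 0.357 (+2.4 points); median 44 weeks.
- One event at each of weeks 20 and 28 recoded: 16/18 × 15/16 × 13/14 × 6/12 = 0.387 (+5.4 points); median 52 weeks.
- Both week-20 events and one week-28 event recoded: 16/18 × 13/14 × 6/12 = 0.413 (+7.9 points); median 52 weeks.

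**4. Size by simulation**

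(a) Assume n = 18, exponential PFS with median 8 months and 18 months' follow-up, so true 12-month PFS is 2^(−12/8) = 0.354. Over 4,000 runs per case, mean 12-month PFS goes from 35.2% to 37.8% with one event recoded (+2.6), 35.5% to 41.0% with two (+5.5) and 35.1% to 43.7% with three (+8.6).

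(b) On the protocol scan weeks, 3,000 runs per case. The share is the assumed proportion of progressing patients irradiated after progression while on study.

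| Cohort, assumed median | Share | Events | 52-week PFS |
|---|---|---|---|
| A, 7 months | 10% | 14.8 → 13.4 | 0.31 → 0.35 |
| A, 7 months | 20% | 14.8 → 11.9 | 0.31 → 0.39 |
| A, 7 months | 30% | 14.8 → 10.3 | 0.31 → 0.45 |
| A, 4 months | 20% | 17.1 → 13.7 | 0.13 → 0.20 |
| A, 12 months | 20% | 11.4 → 9.2 | 0.50 → 0.58 |
| B, 3 months | 20% | 7.9 → 6.3 | 0.085 → 0.16 |

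If an earlier progression takes precedence, these shifts vanish: cohort A at 7 months stays at 14.8 events and 0.31 for every share.

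**5. Prohibited treatment unrelated to prognosis**

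If 25% of cohort A receive such a treatment (assumed; median 7 months), events fall from 14.8 to 13.2 and 52-week PFS stays at 0.31. Here the cost is information, with almost no bias.

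**The case against.** The strongest reply is that the event definition already settles the matter. PFS runs to the first progression or death, so a progression documented before radiotherapy is the event and nothing later can undo it. Many programmers would code it that way. The contrast with bullet 4 also has an innocent explanation: an ipilimumab switch can follow either RECIST progression or clinical progression alone, and the qualifier separates the two. This stands as a fair reading, but the SAP does not state it, and bullet 3 is the only one of the four with no event-status condition.

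Second, the sequence is narrow. Radiotherapy on study is limited to a symptomatic solitary lesion, at the investigator's discretion and after consulting the sponsor (Protocol 6.5.1). Continuing after progression should require no symptoms or signs of progression and no need for alternative treatment (Protocol 5.3, 6.3). A reader might infer that progression followed by on-study radiotherapy is to be expected; the documents show only that it can happen, and give no frequency.

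Third, the reach into medications is limited: only live vaccines are prohibited, acute treatment of immune-related events is exempt, and short courses of low-dose steroids are permitted (Protocol 6.5.2). Read beside radiotherapy, the phrase could mean tumour-directed treatment. That is plausible, but undefined.

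Fourth, the protocol leaves technical detail to the SAP (11.1) and allows deviations to be documented and justified there (11.6). Adding a rule is therefore permissible; what is missing is its justification and its entry in Section 6. The planned listings and counts of censored subjects would also let a reader find any recoded event. Finally, at n = 18 and 12-month PFS near 35%, an approximate 95% interval is 1.96 × √(0.35 × 0.65/18) = ±22 points, wider than the shifts shown.

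**Conclusion.** The point holds as a defect of wording and documentation that can give a wrong PFS result. Read literally, bullet 3 recodes a progression documented before the intervention as censored. Even if earlier progression takes precedence, progression or death after a triggering treatment is dropped, contrary to Protocol 10.2. The rule is undeclared in Section 6, and the SAP plans no PFS sensitivity analysis without it.

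Recoding one to three events in 18 patients raises 12-month PFS by roughly 3 to 9 points. This rests on assumed medians and an assumed number of recoded events; the documents give neither.

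A reader might infer that the plan selectively removes progressions and so inflates PFS. The documents do not support that as a statement of what will happen. Upward bias needs the literal reading together with post-progression intervention, or an intervention prompted by progression. Censoring for a vaccine or steroid course unrelated to prognosis mainly loses events. Nor can the effect on comparability with published data be checked, because the comparator's full censoring rules are not in the documents. The primary endpoint, response rate, is not touched.

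**What to change.** Amend bullet 3 along these lines: *Subjects without prior documented progression by RECIST 1.1 who receive radiotherapy or a new anti-cancer therapy while on study are censored at the last evaluable assessment before it. Progression documented before it remains an event. Other prohibited medications do not censor.* If the sponsor prefers a wider trigger, use the test already in SAP 5.6, prohibited medication judged likely to have affected efficacy. State whether the solitary-lesion radiotherapy that Protocol 6.5.1 may allow falls under the rule.

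Add the rule and its reason to SAP Section 6, and present PFS under the Protocol 10.2 definition as a sensitivity analysis.

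In the scenarios above, the progression condition keeps cohort A at 14.8 events whatever the rate of later radiotherapy, and the narrower trigger restores the 13.2 events to 14.8. The cost is a few sentences and one repeat of the Kaplan-Meier table. PFS may look slightly less favourable.

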Patients in cohort B who fail to respond to treatment with IMM-101 + nivolumab i.e., they have either documented progression by RECIST 1.1, or clinical progression (but without meeting the RECIST 1.1 rules for progressive disease), and, in both cases have no prior recorded response, have the option to change treatment on study to ipilimumab + IMM-101 if the Investigator considers this in the patient's best interest and the patient has not previously received ipilimumab off study (monotherapy or in combination). This treatment may continue until the maximum 4 doses of ipilimumab have been received or stop sooner due to unacceptable side-effects, the Investigator's decision to discontinue treatment, withdrawal of patient consent or 18 months of study treatment, whichever is the sooner. Patients in cohort B who receive all 4 doses of ipilimumab should remain on study after this time and follow the protocol assessments. They may continue to receive IMM-101 during this period until unacceptable side-effects, the Investigator's decision to discontinue treatment, withdrawal of patient consent or 18 months of IMM-101 treatment, whichever is the sooner.

All patients will be followed up for assessment of safety, response to treatment (via scheduled computerised tomography [CT] or magnetic resonance imaging [MRI scans]) and survival, according to the Study Schedule of Assessments with all patients allowed the opportunity of 18 months of treatment on study. The first scheduled post-baseline scan is at week 12 for patients in cohort A and at week 6 for those in cohort B. Subsequent scans are every 8 weeks with unscheduled scans allowed if clinically indicated, for example to confirm progression. At

Page 31 of 98

the discretion of the Investigator, the frequency of scans may be increased to every 12 weeks for patients who continue on study beyond week 52.

Reviews of all available safety data, to include AEs, biochemistry and haematology and injection site reactions, will take place by the Sponsor and Investigator every 6 months throughout the study. Any signals identified that are believed to impact on patient safety may result in termination of the study.

This Phase 2a open-label study will consist of two phases:

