#### 7.5 TREATMENT BEYOND PROGRESSION

Patients in cohorts A and B who have documented disease progression by RECIST 1.1 may continue treatment with IMM-101 + nivolumab on study if they have a clinical benefit and no decline in performance status, no clinically relevant adverse effects with the study treatment as determined by the investigator, or are not deemed to require alternative treatment (See Section 6.3).

Patients in cohort B who fail to respond to treatment with IMM-101 + nivolumab i.e., they have either documented progression by RECIST 1.1, or clinical progression (but without meeting the RECIST 1.1 rules for progressive disease), and, in both cases have no prior recorded response, have the option to change treatment on study to ipilimumab + IMM-101 if the Investigator considers this in the patient's best interest and the patient has not previously received ipilimumab off study (monotherapy or in combination). This treatment may continue until the maximum 4 doses of ipilimumab have been received or stop sooner due to unacceptable side-effects, the Investigator's decision to discontinue treatment, withdrawal of patient consent or 18 months of study treatment, whichever is the sooner. Patients in cohort B who receive all 4 doses of ipilimumab should remain on study after this time and follow the protocol assessments. They may continue to receive IMM-101 during this period until unacceptable side-effects, the Investigator's decision to discontinue treatment, withdrawal of patient consent or 18 months of IMM-101 treatment, whichever is the sooner.

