3 SAMPLE SIZE

Sufficient patients will be screened for 18 patients to be enrolled into cohort A and 8 into cohort B of this open-label study. Patients withdrawn during the course of the

study will not be replaced. No formal sample size calculation has been performed and the sample size is considered a sufficient and adequate number of patients to investigate the efficacy signals of IMM-101 combined with nivolumab in controlling advanced melanoma and to explore the safety profile of the combination therapy.

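### Cohort B PFS censors patients who switch to ipilimumab for clinical progression; this raises the Kaplan-Meier estimate from the switch onward, and no alternative Cohort B PFS analysis is planned

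*SAP*

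**What the plan says.** The censoring rule is in SAP 5.13.2.1: "Subjects in Cohort B who change therapy to IMM-101 + ipilimumab without documented progression by RECIST 1.1 will be censored", with the date set at the last evaluable scan before the change. The protocol has the same rule. In 5.2.2 these patients "will be censored at the date of their last evaluable tumour assessment prior to this change in therapy", and 10.2 repeats it: "will be censored at the date of their last evaluable tumour assessment (scan) prior to this change in therapy".

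Protocol 5.1 (repeated in 7.5) defines who may switch. The group is introduced as "Patients in cohort B who fail to respond to treatment with IMM-101 + nivolumab". It covers patients with documented RECIST 1.1 progression "or clinical progression (but without meeting the RECIST 1.1 rules for progressive disease), and, in both cases have no prior recorded response". The patient must also not have had ipilimumab before the study.

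On size, SAP 3 states "Sufficient patients will be screened for 18 patients to be enrolled into cohort A and 8 into cohort B" and "No formal sample size calculation has been performed".

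Around the PFS analysis, the SAP plans the following:
- the number and percentage censored, and a patient-level time-to-event listing (5.13.2.1);
- a listing of the date and reason for ipilimumab (5.11), and a table of the reasons (5.12);
- a per-protocol repeat of PFS for Cohort A only (5.13.2.1);
- two sensitivity analyses, both on best overall response (5.13.1).

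None of these is a second PFS analysis for Cohort B.

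**The concern.** Kaplan-Meier estimation treats a censored patient as having the same future risk as those still under observation. Under this rule the reason for censoring is that the investigator judged the disease to be progressing. The censoring date is also moved back to the previous scan, which on the 8-weekly schedule can be up to about 8 weeks before the switch.

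The Cohort B PFS estimate is at stake. Protocol 4 and SAP 2.1 say that results will be compared with published data on nivolumab alone. In a descriptive study of 8 patients the curve and its percentiles are the result, and one or two patients can move them visibly.

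**Working it through.** The plan gives no PFS, event or power figure to reproduce. The check covers who is censored, the effect per patient, and how far the estimate could move.

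**1. Who is censored.** A permitted switch follows either RECIST 1.1 progression (a PFS event) or clinical progression only. Remove the first group, and the rule applies only to patients with clinical progression and no prior recorded response.

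**2. Effect per patient.** Let n be the number at risk just after the switcher's last scan, and d the number of other events between that scan and the switch. Assume no other censoring in that gap and someone still at risk after the switch. Relative to the curve at the scan, the estimate just after the switch is:
- switch counted as an event: (n − d − 1)/n
- switcher censored at the scan: (n − 1 − d)/(n − 1)

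The ratio of the second to the first is n/(n − 1), whatever d is. With n at most 8 it is at least 8/7 = 1.14, and it grows as n falls.

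**3. Inside the gap the sign can reverse.** Take 8 at risk after the week 6 scan, a death at week 8 and a clinical switch at week 10. From week 8 to week 10 the curve is 6/7 = 0.857 under the SAP rule and 7/8 = 0.875 if the switch is an event. From week 10 it is 0.857 against 6/8 = 0.750.

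**4. First example (invented data, n = 8).** RECIST progression occurs at weeks 6, 14 and 14, and three patients are event-free to week 30. One patient switches at week 5 before any scan, and one at week 10 with the last scan at week 6. PFS at week 26:
- SAP rule: (6/7) × (3/5) = 0.514
- switches as events: 3/8 = 0.375

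Step 2 gives the same answer: 0.375 × (8/7) × (6/5) = 0.514.

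**5. Second example (invented data, n = 8).** Without clinical switches, events fall at weeks 6, 6, 14, 14, 22, 30 and 46, and one patient is event-free to week 78. Now let k of the patients with events at weeks 14, 14 and 22 instead switch for clinical progression at week 10, after a week 6 scan. Six are at risk after week 6, so the SAP-rule estimate at week 26 is 0.375 × 6/(6 − k).

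| k | Week 26 PFS, event | Week 26 PFS, SAP rule | Median, event | Median, SAP rule |
|---|---|---|---|---|
| 0 | 37.5% | 37.5% | 14 wk | 14 wk |
| 1 | 37.5% | 45.0% | 14 wk | 22 wk |
| 2 | 37.5% | 56.3% | 10 wk | 30 wk |
| 3 | 37.5% | 75.0% | 10 wk | 30 wk |

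**6. Simulation (n = 8, 4,000 trials per row).** The scan times are the protocol's (week 6, then every 8 weeks). Assumptions not in the documents: exponential time to failure, the medians and clinical-only shares shown, and every clinical-only failure switching at once. Mean week 26 PFS:

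| True median | Clinical-only share | Event | SAP rule | Difference (points) |
|---|---|---|---|---|
| 12 wk | 12.5% | 27.4% | 32.1% | 4.7 |
| 12 wk | 25% | 26.4% | 36.7% | 10.3 |
| 12 wk | 50% | 25.5% | 50.3% | 24.8 |
| 20 wk | 12.5% | 45.8% | 50.8% | 5.0 |
| 20 wk | 25% | 45.1% | 55.2% | 10.1 |
| 20 wk | 50% | 43.7% | 67.0% | 23.3 |

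With no clinical-only failures the two analyses agree exactly. In no simulated trial was the median or the week 26 estimate lower under the SAP rule. The curve is carried flat beyond the last follow-up, so the 50% rows are the least secure.

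**The case against.** The case for leaving the plan alone is substantial.

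- **The rule is pre-specified and consistent** across Protocol 5.2.2, Protocol 10.2 and the SAP. The endpoint is PFS by RECIST 1.1, and Protocol 5.3 chose RECIST for comparability with published data. Counting clinical progression as an event changes the endpoint. This stands, and is why the RECIST rule should remain the main analysis.
- **PFS is secondary and everything is descriptive.** No error rate is affected. A reader might infer that a few switchers could decide whether Cohort B shows a signal, but the documents set no PFS threshold or decision rule.
- **The patients are not hidden.** A reader might infer that the plan offers no check at all. It does: the censoring count, the time-to-event listing, and the listing and table of ipilimumab reasons. With 8 patients the alternative curve could be rebuilt by hand. Response rate and disease control keep the full analysis set as denominator, and overall survival is not censored at the switch. What is missing is narrower: a planned alternative PFS analysis, and censoring split by reason. A recalculation after the data are seen is weaker than one specified beforehand.
- **The number affected may be small.** Prior ipilimumab or a recorded response rules out a switch. Unscheduled scans are allowed when clinically indicated; if one shows RECIST progression before the switch, the patient is an event. A switch before the first scan at week 6 is an edge case. This limits the size but not the direction.

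**Conclusion.** The point holds. In Cohort B the rule censors only patients judged to have progressed clinically, so the censoring is informative and the Kaplan-Meier PFS estimate is raised from the switch date onward. The factor is at least 8/7 per such patient with at most 8 at risk, given no other censoring between scan and switch. With no such patients the effect is zero.

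The absolute size cannot be fixed in advance, because the documents do not say how many clinical-only switches to expect. An assumed share of 12.5% to 50% gives a rise of about 5 to 25 percentage points at week 26. That range illustrates the effect and does not forecast it.

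A reader might also infer that the bias is upward at every time point. It is not: between the censoring scan and the switch the curve can be slightly lower, as step 3 of the working shows.

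**What to change.** Keep the RECIST 1.1 censoring rule as the main analysis. In SAP 5.13.2.1:

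1. Add one pre-specified Cohort B sensitivity Kaplan-Meier analysis on the ITT set, in which a switch to ipilimumab for clinical progression counts as an event on the switch date. All other rules stay the same.
2. Report the number censored for PFS by reason, with the ipilimumab switch as its own row.

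The cost is one extra table and curve. SAP 5.11 already lists the date and reason for ipilimumab, so no new data are needed. The downside is that the sensitivity endpoint is not purely RECIST and should be labelled so.

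The analysis should not be extended to patients who stop treatment for clinical progression without switching. That case is not examined here, and the withdrawal reasons in Protocol 6.3 give disease progression without separating clinical from RECIST progression. The change concerns the analysis only and takes no view on when a patient should switch.
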